ECG	X							Consecutive replicate ECGs will be obtained (3 readings), whenever feasible for the patient, at approximately 1-minute intervals.	
Safety Assessments									
Physical Exam	X				X			Physical exam includes weight and BSA measurement.	
Vital Signs	X	X	X	X	X	X		Vital sign measurements include temperature, pulse rate, and blood pressure. On Day 1, obtain vital signs prior to and after the completion of the olaratumab infusion (prior to ifosfamide) and within 1 hour after completion of the ifosfamide infusion. On Days 2-5, obtain vital signs prior to ifosfamide infusion and within 1 hour after completion of the infusion. On Day 8, obtain vital signs prior to and after the completion of the olaratumab infusion.	
Adverse Event Assessment	X	X	X	X	X	X		All AEs considered at least possibly related to study treatment will be followed until resolution, stabilization, return to baseline, or until deemed irreversible.	
Concomitant Medication Assessment	X	X	X	X	X	X			
Laboratory Assessments (See Attachment 2 for details)									
Hematology Profile	X				X	X		Hematology measurements must be collected on Day 15 only during Cycle 1 and Cycle 2.	
Coagulation Profile	X							Perform every other cycle beginning at Cycle 1 Day 1.	
Chemistry Profile	X								
Urinalysis	X							Includes a routine urinalysis, and if clinically indicated, a microscopic analysis. If routine analysis indicates > 2+	

Day	Treatment Period 21-Day Cycles							Comments	
	Cycle 1-n								
	Day 1 ^a	Day 2 ^a	Day 3 ^a	Day 4 ^a	Day 5 ^a	Day 8 ^a	Day 15 ^a		
								proteinuria, then a 24-hour urine must be collected and must demonstrate ≤ 1000 mg of protein in 24 hours, or urine protein/creatinine ratio < 1 , prior to proceeding to the next cycle.	
Pregnancy Test	X							Urine pregnancy test on Day 1 of every cycle or per local practice (whichever is of shorter duration) and at short-term follow-up visit. If the urine pregnancy test performed on Day 1 of the cycle is positive, confirm with a serum pregnancy test.	
Immunogenicity	See Attachment 4 for specific time points.							When possible, an immunogenicity sample will be collected at the same time as the PK sample. If a patient experiences an IRR to olaratumab, blood samples for immunogenicity and PK analysis will be taken at the following time points: (1) as soon as possible after the onset of the IRR, (2) at the resolution of the IRR, and (3) 30 days after the IRR.	
Efficacy Assessments									
Imaging Studies (CT/MRI)	X							Imaging studies and tumor assessments are to be obtained every 2 cycles (± 7 days) until documented progression for patients with CR, PR, or SD. RECIST v1.1 should be used for all tumors with the exception of CNS tumors; RANO or Macdonald criteria should be used for CNS tumors.	
RECIST v1.1, RANO, or Macdonald Tumor Assessments	X								
Other Assessments									
PK Sampling	See Attachment 4 for specific time points								
Biomarker Sampling	X							During treatment, a single sample will be collected prior to dosing at Cycle 3 Day 1.	
Biopsy/Tumor Tissue Submission	X							Optional tumor tissue from biopsy for biomarkers and tumor type. May be collected any time during or after Cycle 1 Day 1.	
Premedication									
Premedication prior to olaratumab administration	X					X		In Cycle 1 (both Day 1 and Day 8 doses), all patients should receive premedication with dexamethasone (or equivalent medication) and an H1 antagonist intravenously 30–60 minutes prior to olaratumab infusion. Additional premedication may be	

Day	Treatment Period 21-Day Cycles							Comments	
	Cycle 1-n								
	Day 1 ^a	Day 2 ^a	Day 3 ^a	Day 4 ^a	Day 5 ^a	Day 8 ^a	Day 15 ^a		
								provided at investigator discretion. For all subsequent cycles, all patients should receive premedication with an H1 antagonist (for example, diphenhydramine) intravenously 30–60 minutes prior to each dose of olaratumab. Additional premedication may be provided at investigator discretion. For a patient who has had a Grade 1 or 2 olaratumab infusion reaction in a previous cycle, patients should be premedicated with antihistamine and glucocorticoid (for example, dexamethasone) intravenously 30–60 minutes prior to olaratumab infusion, and acetaminophen (or equivalent) for all subsequent infusions. Additional premedication may be provided at investigator discretion.	
Mesna Administration	X	X	X	X	X			Administer at a minimum 60% of the ifosfamide dose according to institutional guidelines.	
Clinical Drug Supplies									
Administer olaratumab	X				X				
Administer ifosfamide	X	X	X	X	X			Administer ifosfamide for up to 6 cycles or a cumulative dose of 84 g/m ² . Treatment beyond 84 g/m ² requires consultation with the Lilly CRP/CRS.	

Abbreviations: AE = adverse event; BSA = body surface area; CNS = central nervous system; CR = complete response; CT = computed tomography;

ECG = electrocardiogram; IRR = infusion-related reaction; MRI = magnetic resonance imaging; PK = pharmacokinetics; PR = partial response;

RANO = Response Assessment in Neuro-Oncology; RECIST = Response Evaluation Criteria In Solid Tumors; SD = stable disease.

^a A delay of up to 3 days will be permitted due to holidays, weekends, inclement weather, or other unforeseen circumstances, including unexpected changes in patient schedules, and will not count as a protocol deviation. However, assessments must be done prior to treatments and the interval between cycles may not be less than 21 days. In later cycles, longer delays may be allowed in consultation with Lilly medical representative.

JGDN Study Schedule, Follow-up Assessments (All Parts)

Day	Follow-up		Comments
	Short-Term ^a	Long-Term ^b	
	30 days (± 7) after discontinuation date		
Eligibility Assessments			
Lansky/Karnofsky performance status	X		
ECG	X		Consecutive replicate ECGs will be obtained (3 readings), whenever feasible for the patient, at approximately 1-minute intervals.
ECHO or MUGA	X		For patients on the doxorubicin arm: if doxorubicin cardiotoxicity has been observed, an ECHO or MUGA should be performed at the 30-day follow-up visit. Additional ECHO/MUGA may be performed at the investigator's discretion.
Safety Assessments			
Physical Exam	X		Physical exam includes weight.
Vital Signs	X		Vital sign measurements include temperature, pulse rate, and blood pressure.
Adverse Event Assessment	X		All AEs considered at least possibly-related to study treatment will be followed until resolution, stabilization, return to baseline, or until deemed irreversible.
Concomitant Medication Assessment	X		
Laboratory Assessments (See Attachment 2 for details)			
Hematology Profile	X		
Coagulation Profile	X		
Chemistry Profile	X		
Urinalysis	X		Includes a routine urinalysis, and if clinically indicated, a microscopic analysis.
Pregnancy Test	X		If the urine pregnancy test is positive, confirm with a serum pregnancy test.
Immunogenicity	X		See Attachment 4 for details.

Day	Follow-up		Comments
	Short-Term ^a	Long-Term ^b	
	30 days (± 7) after discontinuation date		
Efficacy Assessments			
Imaging Studies (CT/MRI)	X (if applicable)	X	For patients who have discontinued study treatment due to toxicity or reasons other than progressive disease, imaging studies and tumor assessments are to be obtained every 6 weeks (± 7 days) until progression or initiation of other anticancer therapy. RECIST v1.1 should be used for all tumors with the exception of CNS tumors; RANO or Macdonald criteria should be used for CNS tumors.
RECIST v1.1, RANO, or Macdonald Tumor Assessments	X (if applicable)	X	
Subsequent Anti-Cancer Treatments, and Associated Disease Progression Date		X	For all patients, details on subsequent anticancer treatment (start/stop dates and treatments administered) and first post-study treatment disease progression date should be recorded.
Other Assessments			
PK Sampling	X		See Attachment 4 for details.
Biomarker Sampling	X		

Abbreviations: AE = adverse event; CNS = central nervous system; CRF = case report form; CT = computed tomography; ECG = electrocardiogram; ECHO = echocardiogram; IRR = infusion-related reaction; MRI = magnetic resonance imaging; MUGA = multi-gated acquisition; PK = pharmacokinetics; RANO = Response Assessment in Neuro-Oncology; RECIST = Response Evaluation Criteria In Solid Tumors.

- a **Short-term follow-up** begins the day after the patient and the investigator agree that the patient will no longer continue study treatment and lasts approximately 30 days (± 7 days). The date of this agreement is to be reported on the CRF as the date of discontinuation from study treatment.
- b **Long-term follow-up** begins the day after short-term follow-up is completed. Patients that discontinue study treatment for reasons other than progression will be followed every 6 weeks (± 7 days) until progression.

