The planned duration of treatment is not fixed; patients will remain on study until they fulfill one of the criteria for study discontinuation (Section 6.3). Patients on study treatment who continue to experience clinical benefit and no undue risks may continue olaratumab monotherapy after completion of chemotherapy until one of the criteria for discontinuation is met if deemed medically appropriate in the opinion of the investigator and following discussion and agreement by the medical monitor. This study will enroll a minimum of 24 (maximum of 79) pediatric patients, including a minimum of 10 osteosarcoma patients and 10 rhabdomyosarcoma patients across all treatment arms, if possible. The goal will be to enroll approximately 20 evaluable patients in each combination arm (across Parts A, B, and C) to characterize the safety and PK profile of olaratumab and the respective chemotherapeutic agents, and to inform dose choice for potential later-phase studies.

Refer to [Attachment 1](#) for the Study Schedule.

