7.2.2. Dosing Schedule

If any study drug is discontinued (olaratumab or chemotherapy), the patient will be discontinued from the trial. A change of body weight $\geq 10\%$ (increase or decrease) from baseline will result in re-calculation of dose to be administered.

The following treatments will be administered in this study every 3-week (21-day) ± 3 day cycle ([Table JGDN.7.1](#) and [Table JGDN.7.2](#)).

Part A:

Cycle 1

Olaratumab as IV infusion on Day 1 and Day 8 (at 15 mg/kg)

Cycle 2 and beyond

Olaratumab as IV infusion on Day 1 and Day 8 (at 15mg/kg, or 10 mg/kg if de-escalated),

AND

Doxorubicin as IV infusion on Day 1 and Day 2 (at 37.5 mg/m²; up to 6 cycles or a cumulative dose of 450 mg/m²)

OR

Vincristine as IV on Day 1 and Day 8 (patients ≥ 10 kg: 1.5 mg/m², patients <10 kg: 0.05 mg/kg. Dose is capped at 2 mg) plus irinotecan as IV on Days 1, 2, 3, 4, 5 (at 50 mg/m²),

OR

Ifosfamide as IV on Days 1, 2, 3, 4, and 5 (at 2.8 g/m²; up to 6 cycles or a cumulative dose of 84 g/m²). Treatment beyond 84 g/m² requires consultation with the Lilly CRP/CRS.

Part B:

Cycle 1

Olaratumab as IV infusion on Day 1 and Day 8 (at 20 mg/kg)

Cycle 2 and beyond

Olaratumab as IV infusion on Day 1 and Day 8 (at 20 mg/kg),

AND

Doxorubicin as IV infusion on Day 1 and Day 2 (at 37.5 mg/m²; up to 6 cycles or a cumulative dose of 450 mg/m²)

OR

Vincristine as IV on Day 1 and Day 8 (patients ≥ 10 kg: 1.5 mg/m², patients <10 kg: 0.05 mg/kg. Dose is capped at 2 mg) plus irinotecan as IV on Days 1, 2, 3, 4, 5 (at 50 mg/m²),

OR

Ifosfamide as IV on Days 1, 2, 3, 4, and 5 (at 2.8 g/m²; up to 6 cycles or a cumulative dose of 84 g/m²). Treatment beyond 84 g/m² requires consultation with the Lilly CRP/CRS.

Part C:

All Cycles

Olaratumab as IV infusion on Day 1 and Day 8 (at 20 mg/kg),

AND

Doxorubicin as IV infusion on Day 1 and Day 2 (at 37.5 mg/m²; up to 6 cycles or a cumulative dose of 450 mg/m²)

OR

Vincristine as IV on Day 1 and Day 8 (patients \geq 10 kg: 1.5 mg/m², patients <10 kg: 0.05 mg/kg. Dose is capped at 2 mg) plus irinotecan as IV on Days 1, 2, 3, 4, and 5 (at 50 mg/m²),

OR

Ifosfamide as IV on Days 1, 2, 3, 4, and 5 (at 2.8 g/m²; up to 6 cycles or a cumulative dose of 84 g/m²). Treatment beyond 84 g/m² requires consultation with the Lilly CRP/CRS.

Table JGDN.7.1. Treatment Regimens/Dosing Schedule (Parts A and B)

Study Drug		Dose	Route	Timing

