7.2.4. Dose Adjustments and Delays

In the event that a patient experiences a DLT or a DLT-equivalent (a DLT occurring in Cycle 3 or later of Parts A and B or Cycle 2 or later of Part C), treatment will be interrupted. Dosing can be resumed after resolution of the toxicity to baseline levels at the next lower dose level ([Table JGDN.7.3](#)) already deemed safe upon discussion with the Lilly CRP/CRS. For Grade 3/4 toxicities that are not dose-limiting, see Section [7.2.4.1.2](#) for hematologic toxicities and Section [7.2.4.1.3](#) for nonhematologic toxicities.

Table JGDN.7.3. Olaratumab Dose Levels and Adjustments for Olaratumab-related Toxicities

Dose at Enrollment	Dose Reduction		
	First	Second	Third
Dose level 3	20 mg/kg	15 mg/kg	10 mg/kg
Dose level 2	15 mg/kg	10 mg/kg	discontinue olaratumab
Dose level 1	10 mg/kg	discontinue olaratumab	

In the event of alteration of olaratumab therapy due to an olaratumab-related toxicity, chemotherapy need not be altered, and the planned chemotherapy schedule should be maintained. In the event that olaratumab treatment is discontinued for reason of toxicity, the patient should be discontinued from the study.

Similarly, olaratumab therapy should not be altered for chemotherapy-related toxicity, even if the chemotherapy dose is modified. In the event that chemotherapy is discontinued for reason of toxicity, the patient should be discontinued from the study.

To begin dosing at each cycle, the following criteria must be fulfilled:

- ANC $\geq 750/\text{mm}^3$
- Platelets $\geq 75,000/\text{mm}^3$
- Hemoglobin $\geq 8 \text{ g/dL}$
- Total bilirubin $\leq 1.5 \times \text{ULN}$
- AST and ALT $\leq 3.0 \times \text{ULN}$, or $\leq 5 \times \text{ULN}$ if the transaminase elevation is due to liver metastases
- Any nonhematologic toxicity that are NCI-CTCAE, v4.0 Grade <2 or equivalent severity to baseline

Treatment may be delayed for up to 14 days to allow a patient sufficient time for recovery from study drug-related toxicity.

The following information (in this section and the following subsections) pertains to dose modifications and delays for and management of AEs of concern, which may or may not be associated with olaratumab therapy, including the following:

- IRR (see Section [7.2.4.1.1](#))
- Hematologic toxicity (see Section [7.2.4.1.2](#))
- Nonhematologic toxicity (see Section [7.2.4.1.3](#))

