Day	Treatment Period 21-Day Cycles						Comments	
	Cycle 1		Cycle 2-n					
	Day 1 (±3)	Day 8 (±3)	Day 1 (±3)	Day 2 (±3)	Day 8 (±3)	Day 15 (±3)		
Premedication								
Premedication prior to olaratumab administration	X	X	X		X		
In Cycle 1 (both Day 1 and Day 8 doses), all patients should receive premedication with dexamethasone (or equivalent medication) and an H1 antagonist intravenously 30–60 minutes prior to olaratumab infusion. Additional premedication may be provided at investigator discretion.
 
For all subsequent cycles, all patients should receive premedication with an H1 antagonist (for example, diphenhydramine) intravenously 30–60 minutes prior to each dose of olaratumab. Additional premedication may be provided at investigator discretion.
 
For a patient who has had a Grade 1 or 2 olaratumab infusion reaction in a previous cycle, patients should be premedicated with antihistamine and glucocorticoid (for example, dexamethasone) intravenously 30–60 minutes prior to olaratumab infusion, and acetaminophen (or equivalent) for all subsequent infusions. Additional premedication may be provided at investigator discretion.
	
Administer dexrazoxane			X	X			
Dexrazoxane may be given at 10:1 ratio (dexrazoxane to doxorubicin) prior to doxorubicin on Day 1 and Day 2 at the investigator' discretion.
 
Dexrazoxane is recommended for all patients receiving doxorubicin.
	
Clinical Drug Supplies								
Administer olaratumab	X	X	X		X		When the maximum dose of doxorubicin has been reached, olaratumab will not be continued and the patient should be discontinued from the study.	
Administer doxorubicin			X	X			Doxorubicin to be administered at 37.5 mg/m^2 on Day 1 and Day 2 to be continued for 6 Cycles or a cumulative dose of 450 mg/m^2	

Abbreviations: AE = adverse event; BSA = body surface area; CNS = central nervous system; CR = complete response; CT = computed tomography; ECG = electrocardiogram; ECHO = echocardiogram; IRR = infusion-related reaction; MRI = magnetic resonance imaging; MUGA = multigated acquisition; PK = pharmacokinetics; PR = partial response; RANO = Response Assessment in Neuro-Oncology; RECIST v1.1 = Response Evaluation Criteria In Solid Tumors Version 1.1; SD = stable disease.

JGDN Study Schedule, Treatment Period for Olaratumab in Combination with Doxorubicin (Part C)

Day	Treatment Period 21-Day Cycles				Comments	
	Cycle 1-n					
	Day 1 ^a	Day 2 ^a	Day 8 ^a	Day 15 ^a		
Eligibility Assessments						

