Premedication prior to olaratumab administration	X	X	X					X		In Cycle 1 (both Day 1 and Day 8 doses), all patients should receive premedication with dexamethasone (or equivalent medication) and an H1 antagonist intravenously 30–60 minutes prior to olaratumab infusion. Additional premedication may be provided at investigator discretion. For all subsequent cycles, all patients should receive premedication with an H1 antagonist (for example, diphenhydramine) intravenously 30–60 minutes prior to each dose of olaratumab. Additional premedication may be provided at investigator discretion.	

Day	Treatment Period 21-Day Cycles									Comments	
	Cycle 1		Cycle 2-n								
	Day 1 (±3)	Day 8 (±3)	Day 1 (±3)	Day 2 (±3)	Day 3 (±3)	Day 4 (±3)	Day 5 (±3)	Day 8 (±3)	Day 15 (±3)		
										For a patient who has had a Grade 1 or 2 olaratumab infusion reaction in a previous cycle, patients should be premedicated with antihistamine and glucocorticoid (for example, dexamethasone) intravenously 30–60 minutes prior to olaratumab infusion, and acetaminophen (or equivalent) for all subsequent infusions. Additional premedication may be provided at investigator discretion.	
Mesna Administration			X	X	X	X	X			Administer at a minimum 60% of the ifosfamide dose according to institutional guidelines.	
Clinical Drug Supplies											
Administer olaratumab	X	X	X					X		When the maximum dose of ifosfamide has been reached (or has been discontinued), olaratumab will not be continued and the patient should be discontinued from the study.	
Administer ifosfamide			X	X	X	X	X			Administer ifosfamide for up to 6 cycles or a cumulative dose of 84 g/m ² . Treatment beyond 84 g/m ² requires consultation with the Lilly CRP/CRS.	

Abbreviations: AE = adverse event; BSA = body surface area; CNS = central nervous system; CR = complete response; CT = computed tomography;

ECG = electrocardiogram; IRR = infusion-related reaction; MRI = magnetic resonance imaging; PK = pharmacokinetics; PR = partial response;

RANO = Response Assessment in Neuro-Oncology; RECIST = Response Evaluation Criteria In Solid Tumors; SD = stable disease.

JGDN Study Schedule, Treatment Period for Olaratumab in Combination with Ifosfamide (Part C)

Day	Treatment Period 21-Day Cycles							Comments	
	Cycle 1-n								
	Day 1 ^a	Day 2 ^a	Day 3 ^a	Day 4 ^a	Day 5 ^a	Day 8 ^a	Day 15 ^a		
Eligibility Assessments									
Lansky/Karnofsky performance status	X								

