#### **5.4.2. Patient Disposition**

A detailed description of patient disposition will include:

- Summary of the number of patients who entered into the study, and who received at least one dose of study treatment, by site, dose level, overall.
- The summary of the number (and percent) of patients with the primary reasons for discontinuation from study treatment and patients still receiving treatment by dose level and overall. The discontinuation reasons collected in CRF (eg. AE, PD, death, and etc) will be presented.
- Listing of patient discontinuation.

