### 5.9.1. Study Drug Exposure

Study drug exposure will be summarized based on Safety Population. The summary will include duration of treatment, number of infusions, the number of cycles received per patient, cumulative dose, cumulative dose level, weekly dose intensity, relative dose intensity, by dose cohort and combination arm. Details of study drug administration will be included in patient listings.

Dose modifications and delays will also be summarized.

The exposure formulas are defined below.

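### Protocol rules conflict on olaratumab after the chemotherapy maximum in Parts A and B, and the shortening-fraction entry and stopping levels for doxorubicin overlap

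*Protocol*

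**What the plan says.** **Olaratumab after chemotherapy.** Protocol Section 6.2 says that patients with continuing benefit and no undue risk "may continue olaratumab monotherapy after completion of chemotherapy until one of the criteria for discontinuation is met if deemed medically appropriate" in the investigator's opinion, and "following discussion and agreement by the medical monitor". It names no part or arm.

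The Attachment 1 schedule for doxorubicin in Parts A and B, in the row for giving olaratumab, says: "When the maximum dose of doxorubicin has been reached, olaratumab will not be continued and the patient should be discontinued from the study". The matching ifosfamide schedule says: "When the maximum dose of ifosfamide has been reached (or has been discontinued), olaratumab will not be continued", and likewise takes the patient off the study. The next row of that schedule, Section 7.2.2 and the footnotes to Table JGDN.7.1 all let ifosfamide go past 84 g/m² after consultation with the sponsor. The Part C schedules for both regimens carry no stop line, and vincristine/irinotecan has no stated maximum.

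Two general rules bear on this. Section 7.2.2 says: "If any study drug is discontinued (olaratumab or chemotherapy), the patient will be discontinued from the trial". Section 7.2.4 is narrower: "In the event that chemotherapy is discontinued for reason of toxicity, the patient should be discontinued from the study".

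SAP 5.4.2 summarises "primary reasons for discontinuation from study treatment". SAP 5.9.1 says: "The summary will include duration of treatment, number of infusions, the number of cycles received per patient, cumulative dose".

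**Shortening fraction.** Exclusion [15] in Section 6.1.2 keeps a patient out of the doxorubicin arm if the echocardiographic shortening fraction is under 27%. It asks for MUGA or echocardiogram, not both. Section 7.2.4.2.2 stops doxorubicin after an absolute fall of more than 10%, or if the value is under 29%. The first scan after doxorubicin starts is at the end of Cycle 2 in Parts A and B and before Cycle 3 in Part C.

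**The concern.** In the first pair, one passage permits what another forbids, for the same patient at nearly the same time. A site following Section 6.2 keeps a benefiting child on olaratumab; a site following the schedule takes the child off the study. Duration, infusions, cycles, cumulative dose and recorded reason for stopping would then depend partly on which page was read. SAP 5.5 also counts staying on treatment after a withdrawal criterion as an important deviation, so a patient continued under Section 6.2 with the monitor's agreement could be listed as one.

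In the second pair, the protocol admits a patient who already meets its own level for stopping doxorubicin. That patient can lose doxorubicin and, through Section 7.2.2, the trial, with no change in cardiac function.

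**Working it through.** **Olaratumab after chemotherapy**

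1. Reproduce the stated maxima (Section 7.2.2, Table JGDN.7.1). Doxorubicin: 6 cycles × 2 days × 37.5 mg/m² = 450 mg/m². Ifosfamide: 6 cycles × 5 days × 2.8 g/m² = 84 g/m². Both match, so at full dose finishing six cycles and reaching the maximum coincide.

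2. Place the maximum in time. In Parts A and B, Cycle 1 is monotherapy and the six combination cycles are Cycles 2 to 7. Without delays, doxorubicin reaches 450 mg/m² on Cycle 7 Day 2 and ifosfamide reaches 84 g/m² on Cycle 7 Day 5. Olaratumab is due on Days 1 and 8, so the maximum falls between the two Cycle 7 infusions. The text does not say whether the Day 8 infusion is still given.

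3. Compute both readings. Cycle 7 Day 1 is 6 × 21 = 126 days after the first dose. The SAP formula for duration is (last dose date − first dose date + 21) ÷ 7.

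| | Day 8 not given | Day 8 given |
|---|---|---|
| Infusions | 6 × 2 + 1 = 13 | 7 × 2 = 14 |
| Part A, 15 mg/kg | 13 × 15 = 195 mg/kg | 14 × 15 = 210 mg/kg |
| Part B, 20 mg/kg | 13 × 20 = 260 mg/kg | 14 × 20 = 280 mg/kg |
| SAP duration | (126 + 21) ÷ 7 = 21 weeks | (126 + 7 + 21) ÷ 7 = 22 weeks |

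4. Look for a rule that settles it. Section 6.2 lets continuation run until a Section 6.3 criterion is met. The list in Section 6.3.1 does not include reaching a chemotherapy maximum. Section 7.2.2 would settle it only if completing planned chemotherapy counts as discontinuing it, which is not stated. Section 7.2.4 speaks only of stopping for toxicity.

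**Shortening fraction**

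5. Compare the levels. Entry needs 27% or more and the stop applies below 29%, so the overlap is 27% to <29%, a band of 29 − 27 = 2 points. The LVEF levels in the same sections do not overlap: entry at 50% or more, stop level at 40% or below, a gap of 10 points.

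6. Doxorubicin given by the first on-treatment scan if the reading is unchanged:
   - Parts A and B, end of Cycle 2: 1 × 2 × 37.5 = 75 mg/m²; 75/450 = 16.7%, leaving 375 mg/m².
   - Part C, before Cycle 3: 2 × 2 × 37.5 = 150 mg/m²; 150/450 = 33.3%, leaving 300 mg/m².

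7. Leaving the trial follows from Section 7.2.2. Section 7.2.4.2.2 extends the stop to olaratumab only for LVEF changes.

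**The case against.** Section 6.2 is permissive and needs the monitor's agreement, so a site that stops olaratumab does not breach it. That stands, but the permission is then either empty for these patients or used unevenly. The stop line might also be read as one of the criteria Section 6.2 respects; it is not in Section 6.3.1, and on that reading the option would end as it begins.

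The reach is limited, and this stands. The direct conflict covers two arms in Parts A and B. For ifosfamide the maximum is not firm, because treatment may go further after consultation. The analyses are descriptive, exposure uses doses actually given, and patients who leave without progression are still imaged every 6 weeks, the same interval as every two 21-day cycles. The summaries stay computable; what they lose is a common rule behind them.

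On shortening fraction, both rules can be applied in sequence, so they are not strictly contradictory, and patients followed by MUGA alone are outside the point. Both stand. The overlap remains self-defeating for a patient in the band.

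A reader might infer three stronger things:
- **That the primary endpoint is harmed.** It rests on DLTs and PK exposure matching, and the olaratumab conflict arises in Cycle 7. The first on-treatment scan in Parts A and B is at the end of the combination DLT cycle, and in Part C it comes a full cycle later. As scheduled, the patient has completed the DLT cycle.
- **That all of Part C shares the olaratumab conflict.** Its schedules lack the stop line; only an unsettled reading of Section 7.2.2 would extend it.
- **That a Part C patient in the band is stopped before the first dose.** The pre-Cycle 1 scan may be the screening scan, and Section 7.2.4.2.2 has no wording against starting doxorubicin such as Table JGDN.7.7 has for bilirubin.

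**Conclusion.** Both points hold within those limits. In Parts A and B, Section 6.2 and the doxorubicin and ifosfamide schedules give opposing instructions at the chemotherapy maximum. The stop line ends olaratumab after 13 to 14 infusions, at 21 to 22 weeks by the SAP formula; the other rule has no fixed end. These figures assume full doses and no delays and, for ifosfamide, no agreed treatment beyond 84 g/m². The effect is on exposure and discontinuation summaries.

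For doxorubicin patients followed by echocardiogram, the entry and stopping levels overlap by 2 points. The 75 and 150 mg/m² figures assume full doses and an unchanged reading.

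That the texts conflict or overlap is certain. How many patients are affected cannot be estimated from the documents.

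**What to change.** Three wording changes:

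- Reconcile Section 6.2 with the olaratumab rows of the Parts A and B doxorubicin and ifosfamide schedules. State how the ifosfamide consultation clause fits, and whether the Cycle 7 Day 8 infusion is given.
- Add a sentence to Section 7.2.2 saying whether completing planned chemotherapy counts as discontinuing a study drug.
- Reconcile exclusion [15] with the shortening-fraction level in Section 7.2.4.2.2.

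Which rule or threshold applies is the sponsor's clinical decision. No sample size or analysis method changes. Any later effect on treatment length or the eligible pool depends on that choice and is not estimated here.
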